This is an 8-week trial with a 1 week (week 9) safety follow up visit. Visits will be planned to occur at the screening visit and weeks 0, 1, 2, 3, 4, 6, 8 and 9.

The following activities and/or assessments will be performed at/during the Screening visit (Week -4 to Week 0):

- Obtain written informed consent prior to performing any of the formal screening procedures.
- Administer the M.I.N.I
- Administer the C-SSRS, MADRS, ASEX, HAM-D, HAM-A, DSST, CGI-S, RVLTL, Spontaneous Reported AEs and Sheehan Disability
- Record demographic information
- Obtain medical and surgical and psychiatric history
- Record prior and concomitant medications
- Record vital signs (temperature, heart rate, supine and orthostatic blood pressure), body height and body weight
- Perform a complete physical examination
- Perform a 12-lead ECG

- Collect blood and urine samples for evaluation of standard laboratory safety test (chemistry, hematology, and urinalysis)
- Assess all applicable inclusion and exclusion criteria
- Schedule the baseline visit for those subjects that do not require washout of prohibited medications
- Subjects requiring washout of prohibited medication will be provided washout requirements
 - Subjects in adjunctive quetiapine arm will be permitted to continue their pre-existing antidepressants if FDA approved for depression; if not FDA approved, they will be switched to an FDA approved medication for the duration of the study but will undergo washout of other prohibited medications
- Provide instructions on washout of prohibited medication(s), including the duration of the washout period (if needed)
- Assess for and record AEs and concomitant medications

Once potential eligibility is confirmed, the investigator, or a person designated by the investigator, will contact the subject by telephone at or during the Randomization/Baseline (Week 0):

- Determine appropriate duration of the washout period of prohibited medication(s), taking into account any labeling requirements for tapering of medication dose(s), as well as the minimal washout requirements

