 - Weekly phone calls will include a Symptom Checklist, consistent with symptoms of Major Depression, suicidal risk and adverse events, which the Study Coordinator will review with the subject. Any potential concerns will be reviewed with the subject. Any potential concerns will be discussed with the PI and appropriate interventions for subject safety will be planned. The same symptom checklist and monitoring plan for the subjects will be used at the Duke and the non-Duke site.
- Assess all applicable inclusion and exclusion criteria

- Administer the C-SSRS, MADRS, ASEX, HAM-A, DSST, CGI-S, RVLTL, AES, Spontaneous Reported AEs and Sheehan Disability
- Assess for and record AEs and concomitant medications
- Dispense study medication

The following activities and/or assessments will be performed at Weeks 1 through Weeks 6:

- Assess for and record AEs and concomitant medications
- Administer the C-SSRS, MADRS, ASEX, HAM-A, DSST, CGI-S, RVLTL, AES, Spontaneous Reported AEs and Sheehan Disability
- Collect study medication and review medication compliance
- Dispense study medication

The following activities and/or assessments will be performed at Week 8: End of Study or Early Termination:

- Assess for and record AEs and concomitant medications
- Collect study medication and review medication compliance
- Record vital signs (temperature, heart rate, supine and orthostatic blood pressure), and body weight
- Collect blood and urine samples for evaluation of standard laboratory safety tests
- Administer the C-SSRS, MADRS, ASEX, HAM-A, DSST, CGI-S, RVLTL, AES, Spontaneous Reported AEs and Sheehan Disability
- Perform a 12-lead ECG

The following activities and/or assessments will be performed at the Week 9/ Safety Follow-Up Visit:

- Assess for and record AEs and concomitant medications
- Administer the C-SSRS, Spontaneous Reported AEs and the DSST

After all study assessments has been completed or if the participant completes an early term visit, the participants will be referred back to their outpatient treating physician for

psychiatric care. Participants who are uninsured will be referred to Lincoln Community Health Center or Durham Access. Results of the subject's participation will not be available to the subject before they return to their treating doctor.

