Patient termination will occur if the patient experiences a clinically significant worsening of MADRS scores in two successive visits or any worsening on CSSRS on two consecutive visits, or based on clinician judgment or patient preference.

D. Concomitant Medications and Therapy:

All medications for pre-existing medical conditions will be permitted to continue unchanged provided subjects are on a stable dose of at least 12 weeks. Subjects on prohibited concomitant mood stabilizers or atypical antipsychotics will require a 2-4-week washout of the prohibited medication after the subject meets all eligibility criteria at the screening visit. Washout of prohibited medication will be determined by the $\frac{1}{2}$ life of the drug. Subjects on a minimum of 3 months of stable dose of hypnotics (e.g. zolpidem 10 mg per day or benzodiazepine dose of ≤ 2 mg per day of lorazepam or trazodone ≤ 100 mg per day) will be allowed to continue their hypnotic medication at the same dose. Over the counter medications will be permitted if in the opinion of the investigator, they are not considered to have any significant impact on the study. Any medication that has the potential to cause a clinical significant drug interaction with levomilnacipran ER or quetiapine in the judgment of the investigator will require a washout.

VI. STUDY MEDICATION

A. Description and Dispensing

a. Description and Dispensing

Levomilnacipran and quetiapine will be dispensed/administered at specified study visits.

b. Storage

All study medications will be stored in a double-locked cabinet in the Civitan Building. With available access only to the study investigator and research coordinator.

VII. CLINICAL ASSESSMENTS

Diagnostic Evaluation: The Mini-International Neuropsychiatric Interview (MINI) (version 6.6) for DSM-5 Axis I Disorders to establish diagnosis.

Study Parameters/Efficacy:

Efficacy:

The primary outcome measure will be:

Change from Baseline to end of treatment in Montgomery-Åsberg Depression Rating Scale (MADRS) Total Score.

Secondary outcome will be:

Change from baseline to end of treatment in
Clinical Global Impression Scale- Severity (CGI-S) and Improvement (CGI-I) scores
Hamilton Anxiety Rating Scale (HAM-A) scores
Hamilton Depression Rating Scale (HAM-D) scores
Sheehan Disability Scale (SDS) total score.
Scores on Digit symbol substitution test (DSST)
Scores on Rey's Verbal Learning Test (RVLT).
Scores on Apathy Evaluation Scale (AES).

Safety/Tolerability:

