Using Cohen's d effect size to determine sample size, in Cohen's standard text on statistical power (Cohen, 1988), using the NICE definition of a $d=0.5$ or larger, we obtain an estimated sample size (given a two-sided $\alpha = 0.05$ and $1 - \text{Beta} = 0.800$) of $n= 30$ per arm or 60 for the study. A power analysis was also conducted based on an effect size estimate derived from the drug-placebo difference in primary outcome of MADRS scores in published levomilnacipran trials (Citrome, 2013). The summary of Least square mean change between drug and placebo at 95% CI was -4.9 ($p<.0001$). With a two-tailed $\alpha= 0.05$, a sample size of $n= 60$ provides a power of 0.80.

B. Randomization Method

Randomization will occur with randomly generated computer lists held at the Duke site. This group will assign subjects according to a computer-generated the randomization sequence (without blocking or stratification) for each site. After the study coordinator determines eligibility, the participant will be randomized to one of two different arms. Drug capsules will be placed in standard medicine bottles. Each bottle will be dispensed individually by the study coordinator at the appropriate visit. Rater unblinding will be done at the end of the study after data lock. In case of any AEs or SAEs or other emergencies that require the blind to be broken, the pharmacy will have a 24-hour on call support service.

Power analysis was performed using an internet based software program. The results showed that a sample size of $n=60$ ($n=20$ in each of the 3 groups) could detect a strong effect with $\alpha = .05$, unless the true mean difference is quite minimal.

C. Plan of Data analysis

Subjects will be defined as able to be evaluated by two methods. The primary method will be an intent-to-treat analysis, including those who discontinue drug due to lack of efficacy or due to side effects. The secondary method will be completer analysis. The intent-to-treat (ITT) group will include randomly assigned patients receiving study drug with a post baseline efficacy assessment. The safety population will comprise all patients receiving study drug with a post baseline safety assessment.

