Primary efficacy analysis will be conducted in the ITT population using the last-observation-carried-forward (LOCF) method. Treatment group comparisons will base on changes in MADRS from baseline to week 8/end of treatment from repeated measures ANOVA or analysis-of-covariance (ANCOVA) model containing treatment site, gender and baseline MADRS score included as a covariate.

Secondary efficacy analysis: Repeated measures ANOVA or ANCOVA models will be used to analyze change from baseline in secondary measures. Response and remission rates at end of treatment will be compared using the Cochran-Mantel- Haenszel test. No formal hypothesis testing will be performed on safety data. Safety outcomes will be summarized by treatment group and study visit (observed cases) using descriptive statistics. Any clinically significant findings among patients who terminated early will be discussed separately. All analyses will be conducted using SAS Version 9.1.3 (SAS Institute, Inc.; Cary, North Carolina). Statistical comparisons of efficacy outcomes will be 2-sided and considered significant at $P < .05$. Comparisons for secondary endpoints will be not adjusted for multiplicity.

D. Definition of Evaluable Subject (Safety and Efficacy)

Subjects will be defined as able to be evaluated by two methods. The primary method will be an intent-to-treat analysis, including those who discontinue drug due to lack of efficacy or due to side effects. The secondary method will be completer analysis.

XI: ETHICAL AND REGULATORY CONSIDERATIONS

A. Institutional Committee Approval

Duke University Health Systems Institutional Review Board (DUHS IRB) will need to approve the protocol at the Duke site. [name] site will use an external IRB (e.g. Copernicus, Western) and provide Duke with a copy of its approval.

B. Informed Consent

Participation in this study is voluntary and at no cost to the subjects. All potential participants interested in this study must be thoroughly informed of the details of the study. Prior to study participation in this trial, each subject will have an opportunity to ask questions and will sign an approved informed consent form. The signed consent forms will be filed with the investigator's copies of the Case Report Forms for each subject and a copy provided to the subject. Any subject may voluntarily withdraw from the study at any time without prejudicing treatment.

C. Document Storage and Retention

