All data will be analyzed by the Duke site. The PI and Co-Is are solely responsible for data analysis, interpretation of results, presentation and publication of data produced by this study. The results of this study will be presented at national Conferences (APA, NCDEU) and published in peer reviewed journals (Journal of Clinical Psychiatry).

XII: PUBLICATION PLAN:

Presented at APA Annual meeting 2017, NCDEU annual meeting 2017 and article submitted to Journal of Clinical Psychiatry end 2016.

XIV. SCHEDULE OF EVENTS:
STUDY VISIT SCHEDULE

Test	Week -4 Screening	Week 0: Randomization/ Baseline	Week 1	Week 2	Week 3	Week 4	Week 6	Week 8: End of Study or ET	Week 9: Safety Follow- Up
Informed Consent	X								
Eligibility Criteria	X	X							
Demographic Data	X								
Medical/Surgical History	X								
Physical Exam	X							X	
Vital Signs	X							X	
Blood Samples & Laboratory tests	X							X	
Urine Samples Collect.	X							X	
ECG	X							X	
Psychiatric History/MINI	X								
Prior/concomitant meds	X	X	X	X	X	X	X	X	X
Washout instructions	X	X							
MADRS	X	X	X	X	X	X	X	X	
Columbia Suicide Severity Rating Scale	X	X	X	X	X	X	X	X	X
ASEX	X	X	X	X	X	X	X	X	
HAM-A	X	X	X	X	X	X	X	X	
HAM-D	X								
RVLT	X	X	X	X	X	X	X	X	
Spontaneous Reported AEs	X	X	X	X	X	X	X	X	X
DSST	X	X	X	X	X	X	X	X	
Sheehan Disability	X	X	X	X	X	X	X	X	
CGI-I and CGI-S	X	X	X	X	X	X	X	X	
Adverse event reporting	X	X	X	X	X	X	X	X	X
Drug Dispense/Account/Adjust		X	X	X	X	X	X	X

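### The primary MADRS target is not settled between Week 8 and the last on-treatment score; if Week 8 is meant, LOCF as primary handling of dropout can create, shrink or inflate a difference

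*Combined protocol and SAP*

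**What the plan says.** Section VII, Statistical Evaluation, C (Plan of Data analysis) fixes the handling of dropout: "Primary efficacy analysis will be conducted in the ITT population using the last-observation-carried-forward (LOCF) method". The next sentence gives the time point: "Treatment group comparisons will base on changes in MADRS from baseline to week 8/end of treatment". It then gives the model as a "repeated measures ANOVA or analysis-of-covariance (ANCOVA) model containing treatment site, gender and baseline MADRS score", with no rule for choosing between the two.

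The primary outcome under Clinical Assessments begins "Change from Baseline to end of treatment in Montgomery" and goes on to the MADRS total score. It names no week.

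Section V.C introduces the final treatment visit with "The following activities and/or assessments will be performed at Week 8: End of Study or Early Termination", and the Schedule of Events heads the matching column "Week 8: End of Study or ET". An early exit rating therefore sits in the Week 8 slot. The Week 9 safety visit has no MADRS, so the alternative to Week 8 is the last on-treatment assessment, not the last contact.

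The primary analysis set needs a post-baseline efficacy rating and is described as "including those who discontinue drug due to lack of efficacy or due to side effects". The only other efficacy analysis is in completers. No missing-data assumption, mixed model, imputation method or expected dropout rate appears.

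On visits: "Visits will be planned to occur at the screening visit and weeks 0, 1, 2, 3, 4, 6, 8 and 9". The Schedule of Events marks MADRS at screening and at Weeks 0, 1, 2, 3, 4, 6 and 8.

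**The concern.** Week 8 and last on-treatment score are different questions. The first asks how the arms compare after a full course. The second combines that with when patients left. LOCF answers the second by construction. Read as an answer to the first, it treats a score from Week 1 or Week 4 as if it were the Week 8 score.

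The plan gives reasons to expect outcome-related exits. Section VII.C foresees discontinuation for lack of efficacy and side effects, V.C terminates patients on observed MADRS worsening at successive visits, and the Study Discontinuation/Termination list adds adverse events, noncompliance and withdrawal. The arms also differ in kind: one tapers the SSRI and switches, the other keeps it and adds a drug. Equal dropout cannot be taken for granted. At stake is whether a reported Week 8 difference reflects efficacy or the timing of exit.

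**Working it through.** **Inputs.** From the documents: 30 per arm; post-baseline MADRS at Weeks 1, 2, 3, 4, 6 and 8; two-sided alpha 0.05; and a drug-placebo difference of -4.9 points in the power analysis, used here only as a yardstick. The plan has no figure of its own on this point to reproduce. Assumed, because the documents are silent: a 12-point fall in the reference arm, baseline mean 28, SD 5 rising to 9, correlation 0.85 per two weeks, dropout of 10% to 30%, and linear or early (exponential, time constant 3 weeks) recovery.

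**Closed form.** Let F be an arm's fall by Week 8, p its dropout proportion and s the share of recovery still to come at exit. With dropout unrelated to scores, LOCF estimates the arm's change as -F(1 - p·s). If the last score is equally likely at Weeks 1, 2, 3, 4 and 6, its mean time is 16/5 = 3.2 weeks. Linear recovery then gives s = 1 - 3.2/8 = 0.600. Early recovery gives s = 0.354.

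*No true difference:* bias = (p1 - p0) × 12 × s, against the arm that loses more patients.
- 20% v 10%: 0.10 × 12 × 0.600 = 0.72 (linear); 0.10 × 12 × 0.354 = 0.43 (early).
- 30% v 10%: 0.20 × 12 × 0.600 = 1.44; 0.20 × 12 × 0.354 = 0.85.
- Equal dropout: zero.

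*True difference -4.9 (falls of 16.9 and 12):*
- Equal 20%: -4.9 × (1 - 0.2 × 0.600) = -4.31; -4.9 × (1 - 0.2 × 0.354) = -4.55.
- Better arm 30%, other 10%, linear: -16.9 × 0.82 + 12 × 0.94 = -2.58.
- Better arm 10%, other 30%, linear: -16.9 × 0.94 + 12 × 0.82 = -6.05.

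So LOCF can shrink or inflate a true effect.

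**Simulation.** 18 settings, 4,000 trials each, 30 per arm. LOCF ANCOVA was compared with an unstructured mixed model using Kenward-Roger degrees of freedom. Monte Carlo error is about 0.35 percentage points for type I error and 0.03 points for estimates. Results with no true difference:

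| Dropout | Depends on | Course | LOCF bias | LOCF type I | Mixed model type I |
|---|---|---|---|---|---|
| 20% v 10% | nothing | early | +0.40 | 5.5% | 5.9% |
| 20% v 10% | nothing | linear | +0.74 | 6.7% | 4.8% |
| 20% v 10% | observed change | early | +0.52 | 4.9% | 4.5% |
| 20% v 10% | observed change | linear | +0.80 | 6.8% | 5.4% |
| 30% v 10% | nothing | early | +0.84 | 7.2% | 5.4% |
| 30% v 10% | nothing | linear | +1.43 | 10.8% | 5.4% |
| 30% v 10% | observed change | early | +1.09 | 8.8% | 5.5% |
| 30% v 10% | observed change | linear | +1.67 | 11.7% | 4.4% |

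Mixed-model bias was within 0.04 of zero. Completers were off by -0.48 to -0.49 at 30% v 10% when dropout depended on scores. At equal 20% dropout LOCF was within 0.02 of zero, with type I error 4.7% to 5.5%.

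With a true -4.9 and equal 20% dropout, LOCF gave -4.19 to -4.55 and the mixed model -4.88 to -4.92. LOCF power was 43% to 50% under linear recovery and 54% to 60% under early recovery, against about 59% for the mixed model in both.

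**Separate check.** A second simulation used different code and assumed values (14-point fall; about 17% v 38% dropout depending on observed scores). With no true difference LOCF gave +1.9 (linear) or +1.2 (plateau), the mixed model 0.0 and completers about -0.8. With a true -4.9, LOCF gave -2.1 or -3.2 when the better arm lost more patients, and -6.0 or -5.6 when the worse arm did.

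**The case against.** **The target may be clear enough.** End of treatment, a shared Week 8/Early Termination slot and LOCF can be read together as one target: the Week 8 score, or the last on-treatment score if earlier. On that reading LOCF uses the intended score and the gaps above are not bias. This stands as a limit on the point. It does not remove it, because no section states that reading and the analysis section names Week 8.

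**LOCF is not always biased, nor always conservative.** A reader might infer that it fails whenever scores are still changing. The equal-dropout null results contradict that. Nor does equal dropout always shrink a true effect; that needs a difference that grows over time. If the difference were -6 at exit and -4.9 at Week 8 (assumed), 20% dropout in each arm would give 0.8 × -4.9 + 0.2 × -6 = -5.1, an enlargement.

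**The sizes are assumed.** At 20% v 10% with early recovery there is little or no type I error penalty. The calculations also ignore the Early Termination rating. If it fell midway to the next visit, s would drop to 0.51 or 0.28, and the 30% v 10% bias to 1.23 or 0.67. Smaller, but not gone.

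**The mixed model changes the question and is not uniformly better.** No off-treatment MADRS is described, so it estimates the effect had patients stayed on treatment, while the plan's primary set deliberately includes those who discontinue. When dropout followed the unseen next score at 30% v 10%, it was off by -0.34 to -0.40 (LOCF +0.78 to +1.48; completers -0.76 to -0.86). LOCF had the lower mean squared error in 8 of 18 settings. All of this stands and must be disclosed.

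**Repeated-measures ANOVA is already an option.** It is not a remedy as written: LOCF governs the primary analysis and the model is left open.

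**Conclusion.** The point holds in conditional form. The plan should say which MADRS difference it estimates, and at present it does not. If the answer is Week 8, LOCF is a poor primary method when dropout differs between arms or the difference changes after exit. Under the assumed values its null bias runs from 0.40/4.9 = 8% to 1.67/4.9 = 34% of the planning difference, with clear type I inflation only under linear recovery or the wider dropout gap.

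The documents do not show that dropout will be unequal, which arm would lose more, or how scores evolve. They therefore do not support the inference that this trial's type I error is inflated, or that its result will lean in a known direction. If the last on-treatment score is intended, the defect is one of definition and labelling only.

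**What to change.** 1. In the primary outcome and in VII.C, state the target as the Week 8 difference in MADRS change, and state how discontinuation is treated. Say openly that the mixed model estimates the effect had patients remained on treatment.
2. Replace LOCF with one primary analysis: a mixed model for repeated measures on observed MADRS at Weeks 1, 2, 3, 4, 6 and 8. Include treatment, visit, treatment-by-visit, site, gender, baseline MADRS and baseline-by-visit, with unstructured covariance, a named fallback and small-sample degrees of freedom. The Week 8 contrast is the only primary test.
3. Assign Early Termination MADRS to a visit window by actual date, with a rule for a window that already holds a score. Left in the Week 8 slot, it would carry an early score forward just as LOCF does.
4. Keep the LOCF ANCOVA on the last on-treatment score as a sensitivity analysis, and add one analysis that departs from missing at random.
5. If the last on-treatment score is the intended target, say so and do not present the result as a Week 8 effect.

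**Cost.** Wording and a few lines of code; the visits are already scheduled. The model relies on missing at random. It has 6 × 7/2 = 21 covariance parameters for 60 patients, though all 18 × 4,000 = 72,000 simulated trials converged. The SD of its estimate ran from 4% smaller to 2.24/2.00 = 1.12 times that of LOCF. Patients with no post-baseline rating stay outside the primary set under either method.

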The efficacy of extended-release (ER) levomilnacipran has been established for major depressive disorder (MDD) in doses ranging from 40 mg/day to 120 mg/day (Sambunaris et al, 2014; Asnis et al, 2013). Levomilnacipran is the most noradrenergically active of the SNRI class of antidepressant drugs. Levomilnacipran was found to have twofold greater potency for norepinephrine relative to serotonin reuptake inhibition, and 17 and 27 times higher selectivity for norepinephrine reuptake inhibition compared with venlafaxine and duloxetine, respectively (Auclair et al, 2013).

Cognitive dysfunction in MDD is common and associated with greater impairment in functioning and quality of life. Given the similarities in mechanisms of action, it is possible for levomilnacipran to have beneficial effects on neurocognition. Apathy is considered a disorder of motivation and can occur in neuropsychiatric syndromes as well as depression. It is associated with neurocognitive disturbances and functional impairment. It remains understudied in depression.

Augmentation by adjunctive atypical antipsychotics is recommended as one of the clinical strategies on par with antidepressant switch in the APA guidelines to treat MDD. Quetiapine (extended release) is an atypical antipsychotic approved as adjunct to antidepressants for treatment of MDD in doses between 150-300 mg/day and has been extensively used in clinical practice.

Needs assessment: There is a significant unmet clinical need in terms of patients with MDD who show inadequate response and remission with SSRI treatment. Scientific evidence that guides appropriate treatment strategies in terms of further steps of switching or augmentation of medications will improve clinical care in patients with MDD who do not show adequate response to SSRIs.

II. STUDY OBJECTIVE(S):

Primary:

1. To compare the efficacy and tolerability of switching to levomilnacipran ER (40-120 mg/d) versus augmentation with quetiapine 150-300 mg/day to the patients' existing treatment for patients with inadequate relief on generic SSRIs in patients with MDD.

Secondary:

1. To examine the response and remission rates following the switch from generic SSRI to levomilnacipran ER and augmentation with quetiapine.
2. To examine changes in neurocognitive and apathy measures after switching from SSRI to levomilnacipran and after augmentation with quetiapine in MDD

III. STUDY DESIGN and PLAN:

Methodology:

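### The test for response and remission has no named strata and does not use baseline MADRS, so a chance baseline difference between arms goes uncorrected in these rates (minor)

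*Combined protocol and SAP*

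**What the plan says.** - Study Objectives, secondary objective 1: "To examine the response and remission rates following the switch from generic SSRI to levomilnacipran ER and augmentation with quetiapine".
- Statistical Evaluation, part C (Plan of Data analysis), secondary efficacy paragraph: "Response and remission rates at end of treatment will be compared using the Cochran-Mantel- Haenszel test". No stratification factor or covariate follows.
- Same part, primary efficacy paragraph: the MADRS change is analysed with a "model containing treatment site, gender and baseline MADRS score included as a covariate".
- Statistical Evaluation, part B (Randomization Method): a computer-generated "randomization sequence (without blocking or stratification) for each site".
- Part C, on secondary endpoints: "Comparisons for secondary endpoints will be not adjusted for multiplicity".

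The text defines neither response nor remission. The reference list includes two papers on MADRS remission cut-offs, but the plan adopts no cut-off. MADRS is scored at screening and at baseline (visit procedures and Schedule of Events), so the covariate is already collected.

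**The concern.** A Cochran-Mantel-Haenszel (CMH) test is not fully defined until its strata are named. A single pooled table, strata by site, and strata by site and baseline severity all satisfy the sentence, and each can give a different p-value.

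Under a pooled or a site-only reading, baseline severity plays no part. If remission is an end-of-treatment severity threshold, patients who start with lower scores reach it more easily. Simple randomisation of 60 patients can leave one arm milder at baseline. The primary analysis would correct for that and the rates would not. A reader could then see a remission difference, or a disagreement with the MADRS result, that comes partly from who was allocated where.

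**Working it through.** **The plan's own figure.** The documents give no power for the CMH test. The nearest entry is the sample-size table: 31 per group for response of .45 v .27, power 0.80, two-sided 0.05. The usual two-proportion formula gives

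n = [1.96·√(2·0.36·0.64) + 0.842·√(0.45·0.55 + 0.27·0.73)]² / 0.18² = (1.331 + 0.561)² / 0.0324 ≈ 111 per group.

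The stated 31 is not reproduced; log-rank variants give 80 to 114. At 30 per arm, power is about 0.30 for .45 v .27 and for .33 v .17.

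**How often imbalance arises.** With 30 per arm (Study Population), the difference in mean baseline MADRS, in baseline SDs, has standard deviation √(2/30) = 0.258.
- 0.3 SD or more: 2·P(Z > 0.3/0.258) = 0.245.
- 0.5 SD or more: 2·P(Z > 0.5/0.258) = 0.053.

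**What it does to remission.** Assumed, not in the documents: end MADRS mean 17, SD 9.8, baseline SD 5, remission at 10 or below, baseline-to-end correlation ρ of 0.3 to 0.6. The remission rate is Φ((10 − 17)/9.8) = Φ(−0.714) ≈ 24%. An imbalance of d SD with no drug effect gives a difference of

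Φ(−0.714 + ρd/2) − Φ(−0.714 − ρd/2).
- d = 0.3: 2.8 points (ρ = 0.3) to 5.6 points (ρ = 0.6).
- d = 0.5: 4.6 points to 9.3 points.

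The standard error of the remission difference is √(2·0.24·0.76/30) ≈ 11 points. A separate logistic model for response (assumed odds ratio 0.6 per baseline SD) gives about 6 points at d = 0.5.

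**Error rate.** In simulated null trials of 60 patients, simple randomisation and two sites, the pooled CMH test rejected in 4.5 to 5.2%. A logistic score test with site and baseline rejected in 5.0 to 5.8% (logistic scenarios) or 5.6 to 5.9% (remission model). Among null trials with an imbalance of 0.5 SD or more, at ρ = 0.5, one run gave 10.1% for the pooled test and 5.2% for the adjusted test.

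**Power at the plan's own pairs of rates** (6,000 trials per row, assumed 30 per site, no dropout, assumed odds ratios):

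| Rates | Site OR / baseline OR per SD | Pooled CMH | CMH by site | CMH by site × median baseline | Logistic, site + baseline |
|---|---|---|---|---|---|
| .45 v .27 | 1 / 1 | 0.301 | 0.297 | 0.289 | 0.311 |
| .45 v .27 | 2 / 0.6 | 0.307 | 0.303 | 0.301 | 0.331 |
| .45 v .27 | 3 / 0.4 | 0.306 | 0.314 | 0.317 | 0.361 |
| .33 v .17 | 1 / 1 | 0.289 | 0.285 | 0.277 | 0.300 |
| .33 v .17 | 2 / 0.6 | 0.298 | 0.297 | 0.296 | 0.321 |
| .33 v .17 | 3 / 0.4 | 0.289 | 0.298 | 0.303 | 0.344 |

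Site strata change power by 1 point at most in either direction. Site plus continuous baseline adds 1.0 to 5.5 points here, and 7 at the larger contrast .65 v .30. In the remission model with a 4.9-point MADRS difference, three runs of 4,000 trials gave 31% to 34% (ρ = 0.3), 30% to 35% (0.5) and 30% to 39% (0.6). Each figure carries about 0.7 points of simulation error, and up to about 1 point of each gain is the adjusted test's inflated size.

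**The case against.** The sentence does not say that the test is unstratified. CMH is a stratified method, and site is the obvious unstated stratum. This stands: the fault is that the strata are unspecified, not that the plan chose none.

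A reader might also infer that separate lists per site make an unstratified test invalid. The documents do not support that. The lists are simple sequences without blocking, which impose no restriction that the analysis must reflect, and the simulated error rate is about 5%. Chance imbalance is already part of the 11-point standard error, and an unadjusted analysis is legitimate on average. What remains is that the trial will be read conditionally on an imbalance that is visible in its baseline table.

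The sizes rest on assumed inputs, and this stands too. The 4.9-point effect in the plan is a drug-placebo difference, whereas this trial compares two active strategies. A correlation of 0.6 implies a slope of 0.6 × 9.8/5 = 1.18 end points per baseline point, a strong assumption, so the upper end of each range should be read with caution. If response means a 50% reduction, with an assumed baseline mean of 26 to 34, a 0.3 SD imbalance shifts it by only about 0.5 points at correlation 0.3 and 3 points at 0.5.

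Finally, about 14 remitters (0.24 × 60) is few for a model with three terms. That argues against making the logistic test the lead analysis.

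**Conclusion.** The point holds as a minor one. The plan leaves the CMH strata open and leaves baseline MADRS out of the analysis of secondary objective 1, while using it in the primary model.

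The cost is mainly conditional. In the roughly 5% of trials with an imbalance of 0.5 SD or more, the remission difference carries a shift of about 5 to 9 points under the assumed values. The effect on response depends on its definition and may be smaller. The power forgone is about 0 to 8 points, depending on how prognostic baseline is.

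Two stronger conclusions are tempting and do not follow. The first is that the test loses material power for want of site strata; it does not. The second is that a disagreement between the rates and the MADRS mean could arise only from adjustment; dichotomising a score can produce one by itself. The larger limits are the sample size (power about 0.30 for the plan's own pairs of rates, and 0.49 at d = 0.5 against a stated 0.80) and the missing definitions.

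**What to change.** In the secondary efficacy paragraph of part C:

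- State that response and remission will each be compared with a CMH test stratified by site and by baseline MADRS above or below the pooled median.
- Add, as the supporting adjusted estimate, a logistic regression with treatment, site and continuous baseline MADRS, reported as a standardised risk difference with 95% CI. Add gender, to match the primary model, only if the number of events allows.
- Fix one MADRS-based definition of response and one of remission before data lock.

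This costs a few sentences and a few lines of code, with no new data. There are two drawbacks. The adjusted logistic test runs slightly above 5% at n = 60 (about 5.6 to 5.9% in the remission model), which is why it supports rather than leads. Median strata hold about 5% (4.4 to 4.9% in the logistic null scenarios) but recover only part of the precision: about −1 to +6 points of power in the remission model, and as low as −2 in logistic scenarios where baseline carries no information.
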